#### **6.2.2.1 Early Termination of the Entire Clinical Study**

At any time, the study as a whole may be terminated prematurely if:

- New toxicological or pharmacological findings or safety reports invalidate the earlier positive benefit-risk-assessment.
- Requested by the competent authorities.

#### **6.2.2.2 Early Termination at an Individual Study Center**

At any time, the study may be terminated at an individual center if:

- The center cannot comply with the requirements of the protocol.
- The center cannot comply with GCP standards.
- The center's first patient is not recruited within 24 weeks after initiation of the center.
- The expected recruitment rate is not met.

Should the study be prematurely terminated, all study materials (completed and partially completed eCRFs, IMP, etc.) must be returned to the Sponsor. IMP could be also destroyed at the site according to the local procedures.

## 7 ASSESSMENTS AND METHODS

## 7.1 Demographic and Baseline Information

The following information will be recorded during Screening:

### 7.1.1 Demographic and baseline characteristics

A solid black rectangular bar, likely a placeholder or a redacted section of the document.

### 7.1.2 Medical history and prior/concomitant medications

A series of horizontal black bars of varying lengths, likely representing redacted text or data. The bars are arranged vertically and span the width of the page. Some bars are longer, while others are shorter, indicating different lengths of redacted content.

### 7.1.3 Physical examination

A physical examination should include

Any abnormality identified at Baseline should be recorded in the General Medical History and Baseline Conditions eCRF

Targeted physical examinations should be limited to systems of primary relevance and will only be carried out to follow-up any significant medical condition identified at Screening.

Changes from baseline abnormalities at subsequent visits should be recorded in patient notes. New or worsened clinically significant abnormalities should be recorded as AEs in the Adverse Event eCRF.

#### 7.1.4 Laboratory parameters

## 7.2 Efficacy Assessments

### 7.2.1 Assessments for Primary Efficacy Endpoint(s)

To study improvement of neuropsychiatric symptomatology and behavior in PANS/PANDAS patients, mean changes in the total CY-BOCS score from Baseline to Week 9 will be compared between Panzyga and placebo treatment to demonstrate superiority. The following measurement scores on obsessive-compulsive symptoms will be recorded in investigator-led interviews:

As described in Section 3.3.3, the CY-BOCS yields a total obsession score, a total compulsion score and combined total score (maximum total CY-BOCS score = 40).

## 7.2.2 Assessments for Secondary Efficacy Endpoint(s)

To assess behavioral changes, durability of improvement of neuropsychiatric symptomatology and behavior in PANS patients will be determined with the clinician-rated CY-BOCS score. The mean change in total CY-BOCS score from Week 9 to Week 18 within the (Panzyga – Placebo)

treatment sequence group will be assessed to demonstrate that no statistically significant increase occurred in this period.

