safe and generally well-tolerated. The mean decrease in CY-BOCS score during the double-blind phase was  $24\pm31\%$  in the IVIG group (n=17) and  $12\pm27\%$  in the placebo group (n=18). This difference was not statistically significant (effect size = 0.28, 95% confidence interval - 0.39–0.95), with six responders in the IVIG group (35%) and four responders in the placebo group (22%). Notably, the blinded phase included only one treatment cycle, which might not be enough to show a full effect of treatment and detect a difference between IVIG and placebo. Twenty-four children met criteria for non-response and received open-label treatment (n=10 IVIG, n=14 placebo). Across all participants, a mean CY-BOCS improvement from baseline at week 12 of  $55\pm33\%$  was observed [37]. A number of unanticipated events (multiple patients acquired new GAS infections during the trial), as well as study design issues, may have decreased the effect size of the trial. Further to the above-mentioned reason, in particular, participants may also have over-reported symptom severity in the double-blind portion of the study to increase the possibility of getting open-label IVIG at six weeks.

Since there are scarce data from rigorously designed double-blind controlled trials with IVIG, Octapharma plans to assess the efficacy and safety of Panzyga treatment compared with placebo in PANS patients.

This study will be conducted in accordance with the ethical principles laid down in the Declaration of Helsinki. The study protocol and any subsequent amendment(s) will be submitted to an Independent Ethics Committee (IEC)/Institutional Review Board (IRB) and to the Regulatory Authority. The study will be conducted in compliance with the protocol, good clinical practice (GCP) guidelines, and applicable regulatory requirements.

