### 2.2 Secondary Objectives

The secondary objectives of this study are to:

- verify the sustainability of the reduction of the severity of symptoms in pediatric patients treated with Panzyga.
- assess the efficacy of Panzyga treatment in reducing functional impairment associated with PANS.

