3.2.2. Secondary Target Variables

Efficacy:

CY-BOCS score at the end of the follow-up period at Week 18 will be compared to the Week 9 scores within the (Panzyga – Placebo) treatment group to assess the durability of the clinical benefit associated with Panzyga treatment.

The protocol specifies the following standardized instruments for the assessment of behavioral changes as secondary efficacy endpoints:

- Clinical Global Impression (CGI) – For the confirmatory endpoint analysis the CGI-I (CGI – Improvement) total score will be used
- Parent & Child OC Impact Scale – Revised (COIS-RP and COIS-RC) – For the confirmatory endpoint analysis the COIS-RP total score will be used
- The Swanson, Nolan, and Pelham Rating Scale (SNAP-IV, 26 item)
- Parent Tic Questionnaire (PTQ)

These scores are therefore considered as secondary target variables; please refer to the protocol for details on these instruments.

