It is important to keep in mind that the primary efficacy evaluation of this study will be based on changes in the total CY-BOCS score from Baseline to Week 9, no data collected in the cross-over phase will be considered. Patients dropping out after Week 9 are not considered as withdrawals for the primary objective of the study.

As the first secondary endpoint is to assess the durability of the clinical benefit, this analysis will be based on data collected throughout the whole study on patients receiving Panzyga in the initial, parallel-group phase (baseline to Week 9) of the study, i.e. on patients randomized to treatment sequence Panzyga – Placebo.

Analyses of all subsequent secondary endpoints will be based on data collected during the parallel-group phase of the study only, i.e. up to Week 9.

After █ patients have completed blinded treatment (Visit Week 9), an interim review of the preliminary safety and efficacy data will be conducted by Independent Data Monitoring Committee (IDMC). At this timepoint, the IDMC will independently evaluate all data accrued in this pivotal study to provide a statement on whether emerging data confirm the prospect of direct benefit and positive risk-benefit ratio for PANS patients treated with Panzyga. IDMC confirmation will justify the submission to concerned Health Authorities of additional study protocol(s) evaluating other dose regimens of Panzyga treatment in patients with PANS. The actual numeric results will not be shared with the Sponsor or Investigators to ensure that bias will not affect subsequent study decisions since the data of the first █ patients will be included in the final statistical analysis.

An interim analysis will be performed by an independent statistician after █ patients have completed the initial 9-week treatment period, to verify the initial assumptions, and to allow for the following adaptations in study design:

1. Adaptive enrichment in the study population

The CY-BOCS scores at Visit 9 will be analyzed with respect to the following covariates/sub-groups in order to identify those that exhibit a promising treatment effect. It will then be determined whether future enrollment will be restricted to any (or a combination) of these:

██████████	██████████	██████████
██████████	██████████	██████████
██████████	██████████	██████████
██████████	██████████	██████████
██████████	██████████	██████████

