2. Sample size re-estimation to achieve the desired power of 80% while maintaining the overall type 1 error rate of 2.5%. Please refer to section 6 for details on the sample size determination.

Study enrollment will continue while enough patient data is accrued to conduct the interim analysis. In case the sample size re-assessment does not result in a required total of more than the number of patients already enrolled at the time, enrollment will be stopped but patients already randomized will continue in the study until the planned end, i.e. for 18 weeks.

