Count data (the frequency of an event in a set time period): rate (count per unit time)

Continuous data (measurements on a continuous scale, including quasi-continuous variables): arithmetic mean, standard deviation, median, minimum, maximum

Scales data (Ordinal and Non-ordinal): absolute and relative frequencies

Time-to-event data (how long it takes to observe the outcome of interest: time to event or last evaluation (censored data in case patients are lost to follow-up) and event rate). These parameters might not be tabulated separately, but can be included as an inset into a Kaplan-Meier plot of the product-limit survival function estimates.

Additional descriptive and exploratory statistics, such as geometric means, quartiles or confidence intervals, are included as appropriate. If not mentioned otherwise, confidence intervals are to be understood as two-sided, 95% confidence intervals.

Categorical data will generally be summarized with counts and percentages of patients. The denominator used for the percentage calculation will be clearly defined.

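### Protocol 7.2.2, as worded, takes a non-significant Week 9 to Week 18 CY-BOCS rise as proof of durability, which non-rejection cannot supply

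*Protocol*

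**What the plan says.** One of the two secondary objectives in Protocol 2.2 is to "verify the sustainability of the reduction of the severity of symptoms in pediatric patients treated with Panzyga". Protocol 7.2.2 turns this into a criterion. Durability is determined with the clinician-rated CY-BOCS, and the mean Week 9 to Week 18 change in the Panzyga – Placebo "treatment sequence group will be assessed to demonstrate that no statistically significant increase occurred in this period".

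The other readable endpoint text is neutral. Protocol 3.1.2 and SAP 3.2.2 compare Week 18 with Week 9 within the Panzyga – Placebo "treatment group to assess the durability of the clinical benefit associated with Panzyga treatment" and say nothing about what result would count.

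SAP 4.1 places the endpoint: "As the first secondary endpoint is to assess the durability of the clinical benefit", it uses patients randomized to Panzyga first. It adds: "Analyses of all subsequent secondary endpoints will be based on data collected during the parallel-group phase of the study only". SAP 8.3 states that missing secondary data are not imputed and that their frequency is reported. SAP section 8 promises descriptive summaries of every secondary variable, with confidence intervals where appropriate: "If not mentioned otherwise, confidence intervals are to be understood as two-sided, 95% confidence intervals".

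Protocol 9.2.2 and SAP 10.2, where the test itself would be specified, are redacted.

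**The concern.** The wording makes a failure to reject the null hypothesis of no rise stand as the demonstration. A non-significant result fits unchanged scores, but it equally fits a sizeable loss of benefit that the group was too small or too variable to detect. The incentive also runs the wrong way: each loss of precision, including each missing Week 18 score, makes success more likely for any given true rise. And the criterion does not ask whether there was a benefit at Week 9 to be sustained.

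Durability is the only secondary endpoint that uses data after Week 9, so within the secondary family the sustainability objective depends on this comparison. As 7.2.2 reads, a partial relapse could be reported as demonstrated durability.

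**Working it through.** The readable text gives no sample size, SD, margin, test level or power for this endpoint, so there is no figure of the plan's own to reproduce. The check shows how the criterion behaves under stated assumptions.

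**Inputs**
- Test: paired t-test on the Week 9 to Week 18 change, upper tail 2.5% (one-sided 2.5%, or the upper side of two-sided 5%). This is assumed. SAP 4.1 refers to "Sample size re-estimation to achieve the desired power of 80% while maintaining the overall type 1 error rate of 2.5" percent, but that concerns sizing the trial and not this test.
- Group size n: assumed 20 to 60 patients in the Panzyga – Placebo group.
- SD of the change: assumed 6, 8 or 10 points. The only variability figure for Panzyga's class is in Protocol 1.1, a 24 ± 31% fall with IVIG in an earlier trial. Taking 31% of a baseline of 16, 24 or 30 points gives 5.0, 7.4 or 9.3 points. That SD describes change from baseline, so it is only a rough guide.
- True mean rise Δ: 3 points. For scale, the earlier trial's between-arm difference was 24% − 12% = 12 percentage points. On a baseline of 24 points this is 2.88 points, and the IVIG arm's own fall is 0.24 × 24 = 5.76 points.

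**Step 1: chance that a real rise passes.** With SE = SD/√n and δ = Δ/SE, pass probability = P(T < t(0.975, n−1)), where T is noncentral t with n−1 degrees of freedom and noncentrality δ. The largest observed mean rise that is still non-significant is t × SE. The upper 95% limit at that point is twice this value.

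For SD 8 and Δ = 3:

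| n | SE | δ | t | Passes | Largest non-significant rise (upper limit) |
|---|---|---|---|---|---|
| 20 | 1.789 | 1.677 | 2.093 | 64.3% | 3.74 (7.49) |
| 30 | 1.461 | 2.054 | 2.045 | 49.0% | 2.99 (5.97) |
| 60 | 1.033 | 2.905 | 2.001 | 18.5% | 2.07 (4.13) |

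**Step 2: noise.** At n = 30 and Δ = 3, the pass probability is 24.6% at SD 6, 49.0% at SD 8 and 64.5% at SD 10.

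**Step 3: missing scores.** At SD 8 and Δ = 3, falling from 60 to 50 to 40 observed Week 18 scores raises the pass probability from 18.5% to 26.1% to 36.2%, even if the scores are missing for reasons unrelated to outcome.

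**Step 4: no drug effect.** If Panzyga does nothing and scores are flat from Week 9 to Week 18, then Δ = 0 and the criterion is met 1 − 0.025 = 97.5% of the time, whatever n and SD are.

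**Step 5: what a margin would require.** Requiring the upper limit to lie below a margin M, with a true rise of 0 and 80% power, needs about n = (SD × (1.960 + 0.842)/M)². At SD 8 this is 126 patients for M = 2, 56 for M = 3, 32 for M = 4 and 21 for M = 5. If the true rise equals M, the claim succeeds only 2.5% of the time, whatever n and SD are. These margins are examples, not proposals.

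**The case against.** The strongest reply is that 7.2.2 is an assessments section. The hypothesis, level and any margin belong in Protocol 9.2.2 and SAP 10.2, both redacted. A reader might infer that the plan has no margin for durability. The documents do not support that, because a margin may sit behind the redaction. What stands is that the readable criterion is wrong as worded. If a margin does exist, 7.2.2 disagrees with it.

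Second, the confirmatory weight of this endpoint is not established. SAP 3.2.2 speaks of confirmatory analysis for CGI-I and COIS-RP but not in its durability sentence, and first secondary endpoint may only be list order. Summaries, probable confidence intervals and missing-data counts would let a careful reader see a loss. Exploratory Week 18 results (percentage with PANS improvement, and the CY-BOCS and CGI-I correlation) would add context. This lowers the stakes, but none of it changes what 7.2.2 accepts as a demonstration.

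Third, a reader might tie the size to the primary power and infer that losing half the treatment effect would pass about half the time. With 80% power at one-sided 2.5%, the smallest significant rise is about 1.96/(√2 × 2.80) = 0.495 of the between-arm effect, multiplied by the ratio of the SD of the Week 9 to Week 18 change to the SD of the primary change. The effect size cancels, so everything depends on that ratio, which the documents do not give. Half the effect lost passes 49–51% at a ratio of 1, but 9–10% at 0.6 and 71–72% at 1.4. If the gain is instead the arm's own fall, taken as twice the between-arm difference, losing half of it passes only 2–3% at a ratio of 1. No single figure can be claimed for this trial.

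**Conclusion.** The concern holds for the wording of Protocol 7.2.2. Absence of a significant rise is set as the demonstration of durability, and no other readable passage sets a different criterion. This is an error of inference at any sample size, and it rewards imprecision.

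The size in this trial cannot be determined. The 64%, 49% and 18.5% figures rest on an assumed SD of 8, an assumed 3-point rise, assumed group sizes and a one-sided 2.5% paired t-test. The 97.5% figure needs only the test level and flat scores. The fault does not touch the primary analysis. It should be corrected because it governs the first secondary endpoint, but it does not show that the redacted analysis lacks a proper rule.

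**What to change.** Delete the clause in 7.2.2 that makes non-significance the demonstration, and replace it with wording such as: *The mean Week 9 to Week 18 change in total CY-BOCS in the Panzyga – Placebo group will be reported with its two-sided 95% confidence interval. Durability will be claimed, as a within-group result, only if (a) superiority over placebo at Week 9 has been shown and (b) the upper confidence limit lies below a margin justified by the sponsor and fixed before unblinding. Otherwise the result is presented as estimation, with no durability claim.* Condition (a) is needed because flat scores after no benefit could otherwise satisfy (b).

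If Protocol 9.2.2 or SAP 10.2 already holds a margin, align 7.2.2 with it. If no margin can be justified, estimation alone is a sound outcome.

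The cost is one paragraph of protocol text, matching SAP text and a justified margin. No new data are needed. The claim becomes harder to make and may fail even when scores truly hold, as the patient numbers in the last step of the working show. With no concurrent control for this change, meeting the margin shows that scores held, not why they held.

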### 7.3 Safety Assessments

#### 7.3.1 Assessments for Exploratory Safety Endpoints

### 7.3.2 Adverse Events (AEs)

### 7.3.2.1 Definitions

- **Adverse event (AE):** An AE is any untoward medical occurrence in a study patient which does not necessarily have a causal relationship with this treatment. An AE can therefore be any unfavorable and unintended sign (including an abnormal laboratory finding), symptom, or disease temporally associated with the use of an IMP, whether or not related to the IMP.
- **Adverse drug reaction (ADR):** An ADR is any noxious and unintended response to an IMP related to any dose. The phrase 'response to an IMP' means that a causal relationship between the IMP and an AE carries at least a reasonable possibility, i.e., the relationship cannot be ruled out.
- **Other significant AEs:** Any marked laboratory abnormalities deemed clinically significant or any AEs that lead to an intervention, including withdrawal of drug treatment, dose reduction, or significant additional concomitant therapy.

- **Withdrawal due to AE/ADR:** AE/ADR leading to discontinuation of treatment regardless of treatment arm. Any such events will be followed up by the investigator until the event is resolved or until the medical condition of the patient is stable. All follow-up information collected will be made available to the Sponsor.

### **7.3.2.2 Collection of AEs**

Adverse events will be collected throughout the study from the date of informed consent until the last study visit (end of study) and SAEs will be collected a further four weeks after last IMP dose if the site becomes aware of the event (no proactive monitoring).

The condition of the patient will be monitored throughout the study from the moment that informed consent has been given. During each visit, whether scheduled or unscheduled, AEs will be elicited using a standard non-leading question such as "How have you been since the last visit/during the previous study period?" Adverse events should be collected from the moment that informed consent has been given and at each subsequent visit.

Any AE or ADR which occurs during the study will be noted in detail in the appropriate pages of the eCRF. If the patient reports several signs or symptoms representing a single syndrome or diagnosis, the diagnosis should be recorded in the eCRF. The investigator will grade the severity of all AEs or ADRs (mild, moderate, or severe), the seriousness (non-serious or serious), and the causality as defined in Sections 7.3.2.3, 7.3.3, and 7.3.2.4. The Sponsor is responsible for assessing the expectedness of each ADR (expected or unexpected) as defined in Section 7.3.2.5.

In the event of clinically significant abnormal laboratory findings, the tests will be repeated as deemed necessary by the treating physician and the patient followed up until the laboratory values have returned to normal and/or an adequate explanation for the abnormality has become available.

Diseases, signs and symptoms, and/or laboratory abnormalities already present before informed consent will not be considered AEs unless an exacerbation in intensity or frequency (worsening) occurs.

Fluctuations of PANS/PANDAS symptoms will not be considered untoward medical occurrences and will not be reported as AEs if the investigator deems them to be within the expected range of normal symptom fluctuation or if they do not require concomitant medications or procedures.

The investigator will provide detailed information about any abnormalities and about the nature of and reasons for any action taken as well as any other observations or comments that may be useful for the interpretation and understanding of an AE or ADR.

